7.4.3 Type 1 error control

The overall type 1 error for the study is 5%, which will be used for the efficacy analysis of the dose level assessed in part B of the study. As data from part A of the study will not be used for the main, part B efficacy analysis, no correction for multiplicity or selection is needed.

The unblinded comparative size re-estimation (ubSSR) at the time of part B interim analysis will follow the rules that increase sample size only if comparative results falls in a pre-defined 'promising zone'. Building on the theoretical work of Chen, DeMets and Lan (2004) and Mehta and Pocock (2011), it has been shown that the 'Promising Zone approach' allow type 1 error to be preserved with the use of conventional final analysis test statistic, that is without need for statistical adjustment. To safeguard study integrity, all details regarding the pre-defined ubSSR rules will be documented separately.

The interim analysis will allow only early stopping for futility (non-binding), and not for efficacy, therefore no inflation of type one error is associated with study early stopping criteria.

To protect the overall 5% type I error arising from secondary endpoint multiplicity, all the secondary endpoints will be interpreted inferentially only if a statistically significant treatment effect (p-value ≤0.05) is detected in the primary endpoint for the study.

The order of the secondary endpoints defines an hierarchy according to which these endpoints will be sequentially tested, where an endpoint can be inferentially interpreted only if the previous endpoint was statistically significant. The hierarchy of endpoints will be finalized after Part A data are available but before unblinding of Part A and will be documented in the SAP.

7.5 Safety Analyses

The safety and tolerability of upamostat will be determined by reported AEs, physical examinations, vital signs, and laboratory tests. Patients who receive any study medication, even a partial dose, or who immediately vomit the study medication are considered evaluable for safety.

As noted above, exacerbation of COVID-19-related signs and symptoms are considered lack of efficacy, rather than adverse events. Therefore, hospitalization or death from COVID-19 will be considered in the efficacy rather than safety analyses, although all hospitalizations and deaths, regardless of cause, will be included in the overall statistics for these events. COVID-19-related events will be followed similarly to serious adverse events, but not counted in the analyses thereof.

In part A of the study, safety data will be analyzed per the outline in section 4.8, above, to determine which treatment regimen to carry into part B of the study.

As possible, summaries will be provided for dose level that will be used in both study parts combining data from both parts. Similarly, placebo safety data will be combined. The unselected dose level data will be presented separately.

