This is a randomized, double-blind, placebo-controlled, parallel group study of upamostat compared to placebo in patients with symptomatic COVID-19 who do not require immediate treatment with specific approved (either fully approved or available under emergency use authorization) antiviral or anticytokine therapy, other than therapeutic monoclonal antibodies. The study uses phase 2/3 operationally seamless design methodology for dose selection (part A) and inferentially independent confirmatory phase 3 study (part B). The phase 3 portion will include an interim analysis for revision of the high risk/very high risk subgroup definition, early termination for futility or increase in sample size, as indicated by initial results.

Methodology:

Part A: After qualification for study, patients will be stratified by age, <65 or ≥65, and randomized to treatment as described below. They will then be randomized 1:1:1 to one of the following treatment groups:

- 1. Upamostat 200 mg two capsules qd (n=20);
- 2. Upamostat 200 mg one capsule and matching placebo one capsule qd (n=20)
- 3. Placebo two capsules qd (n=20).

In order to maintain blinding, patients will be given two bottles of medication and instructed to take one pill from each bottle each day. Both pills are to be taken at the same time

Medication should be taken with water and may be taken with or without food.

Patients are to take medication for 14 days or until one of the following occurs:

- Adverse events, whether related or unrelated to study medication which, in the judgement of the investigator, necessitate discontinuation of treatment;
- The patient or investigator decides that it is in the patient's best interest to stop treatment.

An analysis will be performed by a data safety monitoring board (DSMB) after a total of 60 patients complete part A of the study.

- If the DSMB determines that safety of both regimens is similar, accrual in part B will proceed with the 400 mg qd dose.
- If safety is more favorable with the 200 mg qd regimen, accrual in part B will proceed with the 200 mg qd dose.

The DSMB process is further defined in the body of the protocol and will be detailed in a separate DSMB charter. While the DSMB will perform the evaluation at the end of part A independent of the Sponsor, the results will be provided when available in open label fashion to the Sponsor.

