Part B: Based on safety results from part A, either a 200 mg or 400 mg (i.e., one or two 200 mg capsules) treatment regimen will be selected. Patients enrolled in part B will be stratified by

- Presence of one or more high risk characteristics:
 - Age ≥65
 - Hypertension
 - Chronic lung disease (for example, chronic obstructive pulmonary disease, moderate-severe asthma, interstitial lung disease, cystic fibrosis and pulmonary hypertension)
 - Diabetes
 - o Obesity (BMI≥30)
 - Cardiovascular disease (including congenital heart disease, coronary artery disease, history of thrombotic events, including stroke and transient ischemic attacks [TIA])
 - Chronic renal disease
 - o Immunosuppressive disease or immunosuppressive treatment
 - Sickle cell disease
 - Neurodevelopmental disorders (for example, cerebral palsy) or other conditions that confer medical complexity (for example, genetic or metabolic syndromes and severe congenital anomalies)
 - Having a medical-related technological dependence (for example, tracheostomy, gastrostomy, or positive pressure ventilation (not related to COVID-19))
- Planned receipt of therapeutic monoclonal antibody treatment for COVID-19 (whether or not patient has already received the antibody infusion);
- Region in which they are treated; and
- Whether or not the patient is at least 14 days after his or her last dose of COVID-19 vaccine

They will then be randomized 3:2 to active drug or placebo at the schedule selected based on part A. A total of at least 250 patients will be enrolled in part B of the study, at least 150 receiving active drug and at least 100 receiving placebo. Thus, combining both parts of the study, at least 170 patients will receive active drug at the dose selected in part A and at least 120 will receive placebo. However, analyses will be performed independently for parts A and B.

Based on analyses of outcomes at the end of part A and an interim analysis during part B, the risk categories may be adjusted, and the requirements for enrollment may be modified, e.g., a certain percentage of patients may be required to have at least one risk factor and/or some specific combination or number of risk factors.

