All patients who live in regions in which one or more therapeutic monoclonal antibody combinations for outpatient treatment of COVID-19 are available will either be offered antibody, if provided at that facility, or given information as to where they can receive the antibodies. The patient may decide whether or not to take the antibody combination; receipt or refusal of antibody therapy will not affect the patient's participation in this trial. If used, the antibody may be administered before or after the patient starts study medication. However, the patient may not start study medication more than 5 days after onset of symptoms or receipt of laboratory diagnosis of COVID-19, whichever is longer.

In part B, patients will be stratified based on

- 1. The presence of none versus one or more of the above factors,
- Planned receipt vs nonreceipt of therapeutic monoclonal antibodies for COVID-19,
- 3. Region in which patient is treated,

4. Whether the patient is at least 14 days after his or her last dose of COVID-19 vaccine.

and randomized to treatment as described below.

Initially in part B, the proportion of patients in the low risk group, i.e., with no concerning conditions, will be limited to 30%. This number and the definition of high risk, in terms of number and types of risk factors, may be revised at the time of the part A analysis and, in order to enroll a very high risk cohort, again at the interim analysis in part B.

Part A

Initially, a total of 60 patients will be randomized to one of three treatment groups, as follows:

- 1. Upamostat 200 mg two capsules qd (n=20);
- 2. Upamostat 200 mg one capsule and matching placebo one capsule qd (n=20)
- 3. Placebo two capsules qd (n=20).

In order to maintain blinding, patients will be given two bottles of medication and instructed to take one pill from each bottle each day. Both pills are to be taken at the same time.

Part B

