7.2 Analysis Datasets

The primary and most secondary efficacy analyses will be performed on the modified intent to treat (mITT) population, defined as all randomized patients who receive any treatment. A per protocol (PP) analysis will be performed on patients with no major protocol violations and who receive at least one week of study medication or the reason

for stopping medication is worsening COVID-19 or development of AEs. In these analyses patients will be analyzed according to their randomized treatment. Analysis for the first secondary endpoint, hospitalization or death, will be performed primarily on a subset of the mITT population, the high risk or very high risk subset to be defined at the end of part A and redefined at the interim analysis of part B.

Formal efficacy analyses will be performed using part B enrolled subjects, the efficacy data from part A subjects will be descriptively summarized separately.

Safety analyses will be performed on all patients who receive any study medication in parts A and B combined, according to the treatment actually received.

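### Safety data are pooled across parts A and B with no stated adjustment for part, although allocation differs between parts and part A safety drives the dose choice: a small, cheaply fixed weakness in descriptive tables

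*Protocol*

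**What the plan says.** Protocol Section 7.2 defines the safety set across parts: "Safety analyses will be performed on all patients who receive any study medication in parts A and B combined". Section 7.5 then says, with an as-possible qualifier, that "summaries will be provided for dose level that will be used in both study parts combining data from both parts", and adds: "Similarly, placebo safety data will be combined". The dose not carried forward is shown separately. Neither section mentions stratification by part, weighting, or a part B safety table.

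The synopsis (Methodology, Part B) gives the combined totals, "at least 170 patients will receive active drug at the dose selected in part A and at least 120 will receive placebo", but the next sentence says that the parts are analysed independently. It does not limit that statement to efficacy.

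Three features separate the parts:

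- **Allocation.** Part A: "They will then be randomized 1:1:1 to one of the following treatment groups", with 20 per arm. Part B: "They will then be randomized 3:2 to active drug or placebo at the schedule selected based on part A", with at least 150 and 100.
- **Risk mix.** Under Section 4.1, initially in part B "the proportion of patients in the low risk group, i.e., with no concerning conditions, will be limited to 30" percent. No such cap is stated for part A. SAP Section 3 says only that the cap may apply.
- **Monitoring.** Section 1.3 reports that intensive vital sign monitoring was cut back after experience with the first patients.

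Under Section 4.8 the dose is chosen mainly on part A safety. Section 7.4.3 states that "no correction for multiplicity or selection is needed", on the ground that part A data stay out of the part B efficacy analysis.

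**The concern.** A crude pooled percentage in each arm is a weighted mean of the part A and part B rates. The two arms have different weights because allocation changes from 1:1 to 3:2. If adverse event rates differ between parts, the active and placebo columns will differ even when the drug does nothing.

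The second route is selection. The 20 part A patients on the chosen dose helped to get that dose chosen, and they are then counted in its safety profile. The reasoning in Section 7.4.3 does not reach this, because it depends on leaving part A out, and for safety part A is put back in.

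At stake is the table that readers will use to judge tolerability. Descriptive percentages side by side invite comparison whether or not a test is attached. The conflict between the synopsis and Sections 7.2 and 7.5 also leaves the part B SAP, still to be written, without a clear instruction.

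**Working it through.** **Inputs from the documents.** Part A: 20 on the selected dose, 20 on placebo. Part B: 150 and 100, or 225 and 150 if enlarged to 375 at 3:2. Adverse event rates by part and arm are not given, so the rates below are assumptions shown as ranges.

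**1. The plan's own totals.** 20 + 150 = 170 active; 20 + 100 = 120 placebo. Both match the synopsis.

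**2. Share of each pooled arm from part A.** Active 20/170 = 11.8%; placebo 20/120 = 16.7%; gap 4.9 points. With part B at 375: 20/245 = 8.2% and 20/170 = 11.8%; gap 3.6 points.

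**3. Confounding by part, no drug effect.** Active minus placebo = 0.049 × (rate in B − rate in A).

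| Assumed rate in A | Assumed rate in B | Spurious difference (points) | SE of pooled difference (points) |
|---|---|---|---|
| 20% | 30% | +0.49 | 5.40 |
| 20% | 40% | +0.98 | 5.78 |
| 20% | 60% | +1.96 | 5.93 |
| 40% | 20% | −0.98 | 4.97 |

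The ceiling, 4.9 points, needs rates of 0% and 100%.

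**4. Selection.** Assume that both doses have the same true rate. Let 200 mg be chosen only if it has at least k fewer affected patients out of 20 than 400 mg; otherwise 400 mg goes forward. Exact binomial enumeration gives the bias in the chosen part A arm; multiplying by 20/170 gives the bias in the pooled active rate.

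| k | Bias in part A arm at a 30% rate (points) | Pooled bias at 30% (points) | Pooled bias, rates 10% to 50% (points) |
|---|---|---|---|
| 1 | −5.73 | −0.67 | −0.43 to −0.74 |
| 3 | −4.00 | −0.47 | −0.18 to −0.55 |
| 6 | −0.94 | −0.11 | −0.01 to −0.16 |

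Selection makes the active arm look better. If part B has the higher rates, confounding makes it look worse and the two partly cancel. If part A has the higher rates, they add.

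**5. What each remedy does.**

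- *Stratify by part.* Mantel-Haenszel weights are 20×20/40 = 10 for part A and 150×100/250 = 60 for part B, that is 14.3% and 85.7% in both arms. Confounding by part becomes zero. The variance factor is 1/70 = 0.01429, against 1/170 + 1/120 = 0.01422 for crude pooling, so almost no precision is lost. The selection effect stays and weighs slightly more: at 30% and k = 3, −4.00 × 0.143 = −0.57 instead of −0.47.
- *Part B alone.* Both effects vanish. At a 40% rate the SE is √(0.24 × (1/150 + 1/100)) = 6.3 points, against √(0.24 × 0.01422) = 5.8 pooled.
- *Mean squared error at 40%.* Part B alone: 40.0. Crude pool: variance 34.1, plus the squared bias when a 30-point gap between parts (0.049 × 30 = 1.5) and a 0.7-point selection effect act in the same direction, (1.5 + 0.7)² = 4.8; total 39.0.

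**The case against.** The strongest reply is that no pooled drug-placebo difference, interval or test is planned for safety. Section 7.5.1 plans summary tables by treatment group, Section 7.5.2 rules out testing of laboratory data, and SAP Section 15 rules out formal testing in part A. Pooling to see uncommon events is legitimate. Part A safety is analysed separately for the DSMB, the unselected dose stays out of the pool, demographics are summarised by part (Section 7.3), and the part B SAP does not yet exist. All of this stands, and it keeps the point minor. It does not supply part B columns in the final safety tables, nor does it settle the conflict with the synopsis.

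The second reply is that a rate difference between parts is conjecture. This too is largely right. No rates and no part A risk mix are given, part A's low-risk share may already be below 30%, and the SAP makes the cap optional and takes precedence over the protocol. Exacerbation of COVID-19 signs and symptoms, the outcome most tied to risk, is not counted as an adverse event (Section 6.1), and follow-up runs to day 57 in both parts. What remains is that risk mix and monitoring may differ, and that Section 7.5.3 turns clinically significant vital sign changes into adverse events, so detection could differ as well.

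Third, the selection effect is weakened because the synopsis makes 400 mg the default absent marked toxicity differences. Always picking the better-looking of two equal arms would give 0.564 × √(0.3 × 0.7/20) = 5.8 points, or 0.7 after pooling. That is not the plan's rule, and the figure belongs at the top of the range.

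A reader might also infer that the plan guards efficacy, where no selection occurs, and leaves safety exposed. The contrast is too sharp: Section 4.8 and SAP Section 7 let a marked efficacy difference influence the dose.

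**Conclusion.** The weakness is real but minor. Safety is pooled across parts with no stated adjustment, in arms that draw 11.8% and 16.7% of their patients from part A, and the synopsis points the other way on analysing the parts together. Confounding is 4.9% of whatever rate difference exists between parts: about 1 point for an assumed 20-point gap, and about 2 points for 40. Selection adds roughly 0 to 0.7 point, less the more firmly the 400 mg default is applied. Both sit well below a standard error of about 6 points, and all of these sizes rest on assumed rates.

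Two stronger readings are not supported. One is that the pooled safety comparison is materially confounded and biased: the documents give no rates by part and plan no pooled difference. The other is that a part B table should replace the pooled one: on the mean squared errors above, 40.0 against 39.0 even with both biases acting together, part B alone is no more accurate. It is cleaner but less precise, so it belongs beside the pooled table.

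**What to change.** In Protocol Sections 7.2 and 7.5, and in the part B SAP:

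1. Keep the pooled table, labelled as showing total exposure and rare events.
2. Beside it, show part B (150 against 100) and part A by arm as separate columns. The part B columns give the randomised comparison free of both effects.
3. State that any combined active-placebo percentages or difference will be stratified by part with Mantel-Haenszel weights. Say also that this removes confounding by part but not the selection effect.
4. Reconcile the synopsis sentence on independent analysis with Sections 7.2 and 7.5, for example by stating whether it covers efficacy only.

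The cost is wording and extra table columns. The part B columns have a standard error of 6.3 rather than 5.8 points at a 40% rate. Stratifying the combined comparison costs almost nothing in precision. No change to sample size, randomisation or data collection is needed.

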7.5.1 Adverse Events

The NCI-CTCAE v5.0 system will be used to grade new or worsening clinical and laboratory abnormalities. New laboratory abnormalities for which there are no CTCAE v5.0 criteria will be assigned grade 1 if there were no clinical effects or interventions, and according to the criteria in section 6.5 if there were clinical effects and/or interventions. AEs will be grouped and tabulated by MedDRA preferred terms by system organ class.

The Medical Dictionary for Regulatory Activities (MedDRA) version current at time of study initiation will be used to classify all AEs with respect to system organ class and preferred term.

Summary tables of AEs and SAEs will be prepared by system organ class, preferred term and severity for each treatment group. AEs that lead to premature discontinuation from the treatment or to death will be listed separately via data listings.

7.5.2 Clinical Safety Laboratory Tests

Laboratory tests and change from baseline at each time point will be tabulated by treatment groups. No inferential testing will be performed to compare the differences between the treatment groups.

7.5.3 Other Parameters

The results from physical examination will be presented in the subject data listings. Vital signs and physical findings will be shown in listings, but no calculations or study report tables will be generated. Findings on physical examination, including vital signs, which constitute clinically significant changes will be listed as adverse events.

Concomitant medications will be summarized and presented, as will be detailed in the SAP.

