Temperature ^f		Measure and record temperature three times daily until afebrile for 14 days, then once daily in the evening until afebrile for 28 days							
Pulse oximetry ^f	Х	Twice daily through day 15			Thrice weekly through day 29				
Weight	Х								Х
Questionnaire and diary	Х	Every evening days 2-28; days 1, 3, 5 weekly thereafter ^g							
ECG ^h	Х			Х	Х		Х		
Nasal mid-turbinate (NMT) swab for SAR-CoV-2 PCR ⁱ	Х			Х	Х		Х		Х
CBC, biochem profile ^j , D-dimer, INR, PTT				Х	Х		Х		Х
CRP, D-dimer, troponin, ferritin	Х			Х	Х		Х		Х
Serum IgG and IgM antibodies to SARS-CoV-2	Х							С	Х
Alpha-1-antitrypsin and G6PD testing								Ck	X ^k
Study medication		<							
Adverse events ^I			Х	Х	X	Х	Х	Х	Х
Concomitant medications	Х		Х	Х	Х	Х	Х	Х	Х

Abbreviations: BL: Baseline; EOS: end of study; EOT: end of treatment

^aEnd of treatment visit, regardless of actual study day. Should generally be day 15, the day AFTER last dose of study medication.

^bEnd of study visit: generally day 57±4 from start of treatment, regardless of duration of treatment. If patient discontinues study participation prior to then, end of study procedures should be carried out, if possible, at the time of discontinuation from study, even if earlier than day 53.

^cType of contact/location: F: in facility: emergency department, clinic, COVID-19 special facility; H: home visit; H/F: option for either home or facility visit; T: televisit, either phone or video. Note: additional televisits may be arranged as needed. If patient returns to medical facility for outpatient visit, if possible, relevant procedures and tests should be performed at that time.

At all clinic and home health visits, temperature, pulse, respiratory rate, blood pressure, pulse oximetry and ECG measurements will be performed. Home health staff will obtain all vital signs independently of patient measurements, to verify that data are being collected accurately.

^dWithin 3 days prior to planned start of treatment: initial procedures include signing informed consent, review of medical history, review of documentation of COVID-19 disease and source/exposure, if available, height (measured or per patient), pregnancy test for women of childbearing potential, as detailed in section 5.2. When feasible, BL and day 1 procedures, i.e., start of treatment, should be completed on the same day.

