ePhysical examination: physical examination of pertinent systems at baseline, then interim examinations on day 1 of week 2, within 72 h of discontinuation of study medication, study day 29 and within last week of follow-up period. Baseline physical is mandatory for study participation. At each physical examination, a full set of vital signs (temperature, pulse, respiratory rate, blood pressure, and oxygen saturation) will be obtained by the examiner. If one or more on-study visits is not feasible, document in CRF.

The patient will be provided with an electronic thermometer and instructed to measure and record temperature three times daily until afebrile (<38.0°C) for 14 days. Temperature should be measured within an hour of getting up in the morning, between 4-7 pm and within an hour of bedtime each day. Additional temperature readings may be taken at patient initiative or at the instruction of the investigator.

Oxygen saturation will be measured by patients twice daily for the first 2 weeks of study and then three times weekly for the next two weeks. During the first two weeks of study, oxygen saturation should be measured within an hour of arising and within an hour of bedtime, in coordination with the morning and evening temperature readings. After that, oxygen saturation should be measured in the evening, at the time of the evening temperature reading if temperature is still being measured or at the time the patient completes the symptom questionnaire. Additional pulse oximetry readings may be performed at the request of the investigator.

⁹When baseline day = day 1, the patient should not repeat the questionnaire in the evening that day. After day 28 of the study, if a patient does not complete the questionnaire on an assigned day (days 1, 3 and 5 of each week), he or she should complete it during the usual timeframe, 7:00-11:59 pm, on the following day.

^hElectrocardiogram: full 12-lead ECG at baseline visit. At baseline visit and additional days noted, 6-lead ECG is to be performed, either by clinic or home health staff.

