6.1 Terminology

An Adverse Event (AE) is defined as any untoward medical occurrence associated with the use of a drug in humans, whether or not considered drug related. An AE (may also be referred to as an adverse experience) can therefore be any unfavorable and unintended sign (including an abnormal laboratory finding, for example), symptom, or disease temporally associated with the use of a medicinal (investigational or marketed) product, whether or not considered related to the medicinal (investigational or marketed) product and from any route of administration, formulation, or dose, including an overdose. Worsening of baseline signs, symptoms or concomitant illnesses are also considered adverse events.

Exacerbation of COVID-19-related signs and symptoms are considered lack of efficacy, rather than adverse events. All signs and symptoms will be followed, but will be analyzed as part of the efficacy rather than safety analyses.

A Serious Adverse Event (SAE) is any untoward medical occurrence that at any dose results in any of the following outcomes:

death;

is a life-threatening adverse event (defined as an event in which the subject was at risk of death at the time of the event; it does not refer to an event that hypothetically might have caused death if it were more severe);

requires in-patient hospitalization or causes prolongation of existing hospitalization;

a persistent or significant disability/incapacity or substantial disruption of the ability to conduct normal life functions;

a congenital anomaly/birth defect;

is an important medical event. This is defined as a medical event that may not be immediately life-threatening or result in death or hospitalization but, based upon appropriate medical and scientific judgment, may jeopardize the subject and may require medical or surgical intervention to prevent one of the other serious outcomes listed in the definition above. Examples of such events include, but are not limited to, intensive treatment in an emergency room or at home for allergic bronchospasm; blood dyscrasias or convulsions that do not result in hospitalization.

If either the sponsor or investigator believes that the event is serious, the event must be considered serious and be evaluated by the Sponsor for expedited reporting.

A *suspected adverse reaction* means any adverse event for which there is a reasonable possibility that the drug caused the adverse event.

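### Vital signs are named as a basis for judging safety, but no by-arm summary of pulse, blood pressure or respiratory rate is planned

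*Protocol*

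**What the plan says.** On what safety rests, protocol 7.5 states: "The safety and tolerability of upamostat will be determined by reported AEs, physical examinations, vital signs, and laboratory tests". SAP 15 repeats the sentence.

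On collection, the notes to protocol Table 1 say: "At all clinic and home health visits, temperature, pulse, respiratory rate, blood pressure, pulse oximetry and ECG measurements will be performed". They also say that at each physical examination "a full set of vital signs (temperature, pulse, respiratory rate, blood pressure, and oxygen saturation) will be obtained by the examiner". After baseline these examinations are "interim examinations on day 1 of week 2, within 72 h of discontinuation of study medication, study day 29 and within last week of follow-up", which Table 1 shows as days 8, 15, 29 and 57.

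On analysis, protocol 7.5.3 and SAP 16.2 both say: "Vital signs and physical findings will be shown in listings, but no calculations or study report tables will be generated". The next sentence in both gives the route by which a vital sign can reach a table: "Findings on physical examination, including vital signs, which constitute clinically significant changes will be listed as adverse events". Protocol 7.5.1 then provides: "Summary tables of AEs and SAEs will be prepared by system organ class, preferred term and severity for each treatment group".

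That route has a limit. Protocol 6.1 says: "Exacerbation of COVID-19-related signs and symptoms are considered lack of efficacy, rather than adverse events".

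**The concern.** Measures that the plan says will help determine safety are collected by staff at five scheduled visits, and the plan then excludes any summary of them by treatment group. For pulse, blood pressure and respiratory rate, the only way into a table is for an investigator, blinded and looking at one patient, to call a change clinically significant and report it. That suits large individual changes. It does not suit a modest shift in the group average that is unremarkable in each patient.

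At stake is whether the final report can put bounds on an average effect on these measures. Listings hold the raw values but give no estimate and no interval.

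**Working it through.** The plan states no figure on this point, so there is none to reproduce. The check has three parts.

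**1. How each measure is handled**

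| Measure | By-arm summary planned? | Where |
|---|---|---|
| Laboratory tests | Yes: value and change from baseline, no testing | Protocol 7.5.2, SAP 16.1 |
| ECG intervals | Calculation of shifts is referred to | SAP 4.6 |
| Oxygen saturation | Yes: weekly medians, descriptive tables and plots | SAP 13 |
| Temperature | Enters the recovery endpoint | Protocol 7.4.1, SAP 12 |
| Pulse, blood pressure, respiratory rate | No: listings only | Protocol 7.5.3, SAP 16.2 |

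Laboratory tests also have a numerical rule for becoming an adverse event: a change of at least one CTCAE grade (protocol 6.5). No threshold is given for a clinically significant change in a vital sign.

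The volume left in listings is at most 60 × 5 visits × 4 values (pulse, systolic, diastolic, respiratory rate) = 1,200 in part A and 250 × 5 × 4 = 5,000 in part B. Full attendance is assumed.

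**2. What a by-arm table would give**

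Inputs: 20 per arm in part A and 150 versus 100 in part B (protocol 7.1). The SD of change in systolic pressure is not in the documents; 12 to 15 mmHg is assumed.

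95% CI half-width = 1.96 × SD × √(1/n₁ + 1/n₂)

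- Part B: √(1/150 + 1/100) = 0.1291. SD 12 gives 3.04 mmHg; SD 15 gives 3.80 mmHg.
- Part A: √(1/20 + 1/20) = 0.3162. SD 12 gives 7.44 mmHg; SD 15 gives 9.30 mmHg.
- Both parts combined for the selected dose and placebo, as protocol 7.5 intends for safety (at least 170 versus 120): √(1/170 + 1/120) = 0.1192, giving 2.80 to 3.51 mmHg.

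**3. How much the adverse event route would recover**

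This is an illustration with assumed values: pulse mean 80 and SD 12 bpm, and a true average shift of 5 bpm.

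- Comparing means in part B: 5 / (12 × 0.1291) = 3.23, and 3.23 − 1.96 = 1.27, so power is about 90%. At 20 versus 20 it is 26%.
- Counting patients above 100 bpm, an assumed reporting level: 4.8% on placebo and 10.6% on active. Power for 100 versus 150 is about 36% (normal approximation, pooled variance under the null).
- Counting patients above 110 bpm: 0.6% and 1.9%, power about 10%.

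No test is proposed. The powers only show how much information on an average shift is lost when values are reduced to reported events.

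**The case against.** The best defence is that the adverse event tables already cover what matters. Clinically significant vital-sign changes are reported as adverse events and tabulated by arm and severity, and patient listings are produced. This stands for marked changes. A reader might infer that a drug effect on vital signs could not be seen at all, and the documents do not support that. What the route misses is a shift below an undefined reporting level, or one attributed to COVID-19.

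A reader might also infer that all vital signs are shut out of calculation. They are not, since oxygen saturation is tabulated and temperature feeds the recovery endpoint. Nor is respiratory safety unexamined: pneumonia, diary dyspnea and cough, and supplemental oxygen and ventilator use are all analysed. The gap is respiratory rate itself, with pulse and blood pressure.

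A third tempting reading is that the part A dose choice is undermined. Protocol 7.5 sends that choice to the list in protocol 4.8 (SAP 7), which does not name pulse, blood pressure or respiratory rate. The DSMB charter is a separate document, so what else the board receives is unknown. At 20 per arm the estimate would be too wide to help much.

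It can also be said that listing-only handling is stated openly and identically in both documents, that the earlier upamostat experience summarised in protocol 1.2 mentions no pulse or blood pressure signal, and that SAP 16.2 governs part A only. All true. But protocol 7.5.3 covers both parts, so a part B SAP that follows it would repeat the exclusion. Neither document gives a reason for treating these measures differently from laboratory tests.

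**Conclusion.** The point holds in limited form. Protocol 7.5 and SAP 15 make vital signs a basis for the safety judgement, while protocol 7.5.3 and SAP 16.2 rule out any by-arm summary of pulse, blood pressure and respiratory rate. An average drug-placebo difference in these measures that stays below the undefined level of clinical significance, or is classed as COVID-19 exacerbation, would not be shown.

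The loss falls mainly on the part B safety conclusion, where an arm difference in systolic pressure could be estimated to within about 3.0 to 3.8 mmHg and the plan provides no estimate. The part A loss is small (7.4 to 9.3 mmHg). These widths rest on the assumed SD of 12 to 15 mmHg and on complete data. The finding that no summary is planned rests on the text alone.

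**What to change.** In protocol 7.5.3 and SAP 16.2, replace the exclusion for pulse, systolic and diastolic pressure and respiratory rate with a descriptive table by arm and visit (baseline, days 8, 15, 29 and 57) showing value and change from baseline. Use the staff measurements and make no hypothesis test, as already planned for laboratory tests. Carry the same wording into the part B SAP. Physical-examination findings can stay as listings.

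The cost is a wording change and one standard set of tables from data already collected. The downside is slightly more output. No visit, procedure or sample size changes.
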